##### All-cause Joint Replacements

The number and percentage of patients with all-cause joint replacements will be presented by treatment group for the, Treatment and Follow-up Periods both Year 1 and Year 2. The number of replacements in joints that were positively adjudicated will be summarized by treatment

group. Joint replacements will also be summarized by KL score of the affected joint at screening.

The time to JR is calculated as:

$$= (\text{Date of JR} - \text{Date of first dose of study drug in Year 1}) + 1$$

Plots of the Kaplan Meier curves by treatment group (as randomized to in Year 1) of time to JR will be presented based on the SAF – Year 1. Patients without an event will be censored at the last contact.

### **Data from Urgent Safety Measure Patients**

Limited safety summaries will be presented based on the USM Analysis Set including TEAEs and summaries of AAs, DAs and all joint replacements.

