#### **Population**

#### Sample Size:

Enrollment of approximately 2845 patients is planned for this study, which includes a total of 285 patients who were enrolled in the fasinumab 3 mg SC Q4W and 6 mg SC Q8W groups under earlier versions of the protocol before dosing was discontinued due to the urgent safety measure, and a total of approximately 2560 patients who will be randomized to fasinumab 1 mg SC Q4W, 1 mg SC Q8W, naproxen, and placebo.

Approximately 840 patients will be randomized to the fasinumab 1 mg SC Q4W group, 840 patients to the naproxen-only group, and 280 patients to the placebo group. An estimated 600 patients will be randomized to the fasinumab 1 mg Q8W group.

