In the phase 2/3 study of fasinumab in patients with pain due to OA of the knee or hip (R475-PN-1227), 26 AA events occurred in 24 patients. There was an increase in AA events that appeared to be related to greater fasinumab dose. Although these events were milder than the severe DA events presented at the 2012 FDA Arthritis Advisory Committee, in consideration of the lack of an observed dose response for efficacy in OA, the benefit-risk ratio was deemed unfavorable for the fasinumab 6 mg Q4W and 9 mg Q4W doses in patients with OA, in comparison to the other fasinumab doses that were studied (ie, 1 mg Q4W and 3 mg Q4W). The dose regimens that were being evaluated in the phase 3 studies for OA pain in the knee or hip included 1 mg Q8W, 1 mg Q4W, 3 mg Q4W, and 6 mg Q8W. In April 2018, the independent Data Monitoring Committee (DMC) recommended discontinuing 6 mg Q8W and 3 mg Q4W (expected to have similar exposure to 6 mg Q8W) based on a review of unblinded data in an ongoing study in the fasinumab phase 3 OA program (R475-PN-1523). Subsequently, a small Regeneron team reviewed the data and agreed with this recommendation. The DMC noted imbalances in clinically relevant adverse events including time to total joint replacement, peripheral edema, arthralgia and a trend towards early fractures. The phase 3 program for OA pain in the hip or knee continued to evaluate fasinumab 1 mg with the highest dose regimen of 1 mg Q4W. In August 2020, the independent DMC recommended termination of the fasinumab program. The recommendation was based on a review of the totality of evidence, including the emerging unblinded data. Based on the independent DMC recommendation, the sponsor has discontinued dosing with fasinumab. At the time of this recommendation and amendment, the only patients to be impacted are the patients participating in the optional Year 2 portion of the R475-OA-1611 study. These patients will be encouraged to enter the Year 2 safety follow-up period.

Fasinumab is currently being evaluated in a phase 3 trial (R475-PN-1523) designed to assess the long-term safety and efficacy of multiple doses of fasinumab in patients with OA. The phase 3 study described here, R475-OA-1611, is designed to compare the efficacy and safety of fasinumab with those of placebo and of naproxen, a standard-of-care NSAID for moderate-to-severe pain due to OA.

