#### 5.1.3. Randomization

Enrollment of approximately 2845 patients is planned for this study, which includes a total of 285 patients who were enrolled in the fasinumab 3 mg SC Q4W and 6 mg SC Q8W groups under earlier versions of the protocol before dosing was discontinued due to the urgent safety measure, and a total of approximately 2560 patients who will be randomized to fasinumab 1 mg SC Q4W, 1 mg SC Q8W, naproxen, and placebo.

At the baseline visit of Year 1, patients will be randomized 3:3:3:1 to the following treatment groups as follows:

- Fasinumab 1 mg SC Q4W
- Fasinumab 1 mg SC Q8W
- Naproxen 500 mg oral, twice daily
- Placebo

Prior to amendment 5 global, it is estimated that approximately 560 patients were randomized as follows: 240 patients to the fasinumab 1 mg SC Q4W group, 240 patients to the naproxen-only group and 80 patients to the placebo group. Under amendment 5 global, a further 2000 patients were planned to be randomized as follows: 600 patients to the fasinumab 1 mg SC Q4W group, 600 patients to the naproxen-only group, 200 patients to the placebo group, and 600 patients to the newly added fasinumab 1 mg SC Q8W group. Thus, overall, this study will enroll approximately 2560 patients as follows: 840 patients to the fasinumab 1 mg SC Q4W group, 600 patients to the 1 mg SC Q8W group, 840 patients to the naproxen group, and 280 patients to the placebo group.

Prior to amendment 5 global, approximately 285 patients were enrolled in the fasinumab 3 mg SC Q4W and fasinumab 6 mg SC Q8W groups. However, dosing in these patients was discontinued, as recommended by the independent DMC in April 2018.

Patients will receive treatment as described in Section 7.1. Randomization will be stratified according to the affected index joint (hip or knee), the K-L score (2 to 3 or 4) at the screening visit, and geographical region.

Eligible patients who choose to participate in Year 2 will not be re-randomized at week 52. See Section 7.1 for treatment assignments in Year 2.

#### 5.1.4. Treatment Period for Year 1

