**Figure 1: Study Flow Diagram**

Abbreviation: EOS- End of study

Prior to Protocol R475-OA-1611 Amendment 4 Global, patients were randomized 3:3:3:3:1 to receive one of the following treatment regimens:

- Fasinumab 1 mg Q4W - Fasinumab 1 mg SC Q4W and naproxen-matching placebo oral, twice daily
- Fasinumab 3 mg Q4W - Fasinumab 3 mg SC Q4W and naproxen-matching placebo oral, twice daily
- Fasinumab 6 mg Q8W - Fasinumab 6 mg SC Q8W (patients received placebo injections at the study visits where study drug was not administered) and naproxen-matching placebo oral, twice daily

- Naproxen - Fasinumab-matching placebo SC Q4W and naproxen 500 mg oral, twice daily
- Placebo - Fasinumab-matching placebo SC Q4W and naproxen-matching placebo oral, twice daily

A total of 285 patients were enrolled in the fasinumab 3 mg SC Q4W and fasinumab 6 mg SC Q8W groups. However, dosing in these patients was discontinued, as recommended by the independent Data Monitoring Committee (DMC) in April 2018.

Post Protocol R475-OA-1611 Amendment 5 Global approximately 2,560 patients were planned to be randomized 3:3:3:1 to receive:

- Fasinumab 1 mg Q4W - Fasinumab 1 mg SC Q4W and naproxen-matching placebo oral, twice daily
- Fasinumab 1 mg Q8W - Fasinumab 1 mg SC Q8W (patients received placebo injections at the study visits where study drug was not administered) and naproxen-matching placebo oral, twice daily
- Naproxen - Fasinumab-matching placebo SC Q4W and naproxen 500 mg oral, twice daily
- Placebo - Fasinumab-matching placebo SC Q4W and naproxen-matching placebo oral, twice daily

Randomization was stratified according to the affected index joint (hip or knee), the K-L score (2 to 3, or 4) at the screening visit, and geographical region (Europe, North America, and Rest of the World [South Africa]).

Protocol R475-OA-1611 Amendment 6 provided patients the option to continue in the study and receive treatment for an additional year (Year 2). The treatment arm the patients were assigned in Year 2 was determined by the treatment arm they were randomized to in Year 1 according to the following rules:

- Patients randomized to receive Placebo or Naproxen in Year 1 will be assigned to receive Naproxen prn during Year 2
- Patients randomized to received Fasinumab 1 mg Q4W in Year 1 will be assigned to remain on this dose for Year 2
- Patients randomized to received Fasinumab 1 mg Q8W in Year 1 will be assigned to remain on this dose for Year 2

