### **3.5. The Urgent Safety Measure Set (USMS)**

The USMS will include all patients randomized to fasinumab 3 mg Q4W or 6 mg Q8W and is based on the treatment allocated (as randomized). The USMS will be utilized for all analyses of data collected from its included patients.

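### Safety of the stopped 3 mg Q4W and 6 mg Q8W arms is reported without the patients randomised alongside them, so the trial's randomised comparison for these doses goes unreported and crude percentages could understate risk

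*SAP*

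**What the plan says.** SAP 3.5 (and Protocol 10.3.5) defines the Urgent Safety Measure Set (USMS) by the stopped arms alone: "The USMS will include all patients randomized to fasinumab 3 mg Q4W or 6 mg Q8W". It adds: "The USMS will be utilized for all analyses of data collected from its included patients". SAP 3.1 takes these patients out of the FAS. SAP 3.4 draws SAF – Year 1 from the FAS, so they leave the main safety set as well.

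In SAP 5.8.7, adjudicated arthropathy (AA) is summarised on the SAF, with Kaplan-Meier and a descriptive Cox model against placebo. Destructive arthropathy (DA) gets the same methods, and joint replacement (JR) gets Kaplan-Meier curves on SAF – Year 1. For the stopped arms the same section says only: "Limited safety summaries will be presented based on the USM Analysis Set including TEAEs and summaries of AAs, DAs and all joint replacements". It names no comparator, person-time rate, time-to-event method or common window.

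SAP 2.1 gives the size of the group: "A total of 285 patients were enrolled in the fasinumab 3 mg SC Q4W and fasinumab 6 mg SC Q8W groups". It also gives the allocation then in force: "patients were randomized 3:3:3:3:1 to receive one of the following treatment regimens", the regimens being 1 mg Q4W, 3 mg Q4W, 6 mg Q8W, naproxen and placebo.

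**The concern.** Joint harm at higher doses is a central safety question for this drug. Of the earlier phase 2/3 study, Protocol 1.1 says: "There was an increase in AA events that appeared to be related to greater fasinumab dose". The two arms were stopped because of an imbalance seen in a different study (Protocol 3.2.2). This trial has its own randomised patients at those doses, with randomised controls, and its safety objectives (SAP 1.2.2, items 3 to 5) compare fasinumab with naproxen without naming a dose. As planned, that comparison is not reported for the stopped doses.

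A reader who wants a comparison will set the USMS percentages beside the SAF – Year 1 tables. Those arms include patients randomised later and were planned for 52 weeks of treatment, whereas dosing in the stopped arms was cut short and patients moved into follow-up (Protocol 7.1). The treatment-emergent window closes 4 weeks after the last SC dose (SAP 5), and AE percentages are per patient, not per unit of time (SAP 5.8.1). Less time at risk gives a lower crude percentage for the same hazard.

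**Working it through.** **1. Enrolment figures.** The protocol's total is "Enrollment of approximately 2845 patients is planned for this study". The parts agree: 840 + 600 + 840 + 280 = 2560, and 285 + 2560 = 2845.

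**2. Concurrent patients.** Two arms with weight 3 each share 285 patients, so 285/2 = 142.5 per arm. The ratio then implies 142.5 on 1 mg Q4W, 142.5 on naproxen and 142.5/3 = 47.5 on placebo, or 332.5 in all.

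**3. Boundary of the scheme.** SAP 2.1 says 3:3:3:3:1 applied before Amendment 4. The protocol synopsis (Treatments) and Protocol 7.5 say before Amendment 5. Protocol 5.1.3 estimates, before Amendment 5, "240 patients to the fasinumab 1 mg SC Q4W group, 240 patients to the naproxen-only group and 80 patients to the placebo group". If all 560 had been randomised under 3:3:3:3:1, the stopped arms would hold 2 × 240 = 480 patients, not 285. About 560 − 332.5 = 227.5 retained-arm patients therefore appear to have been randomised after those arms closed. This fits the SAP's boundary better, but the documents need reconciling.

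**4. Effect of shorter exposure.** Time on treatment in the stopped arms is not given, so I assume T = 8 to 36 weeks and a constant hazard. Crude risk is 1 − exp(−HR × annual rate × weeks/52). With a control rate of 5% per year, HR 2 and T = 16:
- On treatment: 1 − exp(−2 × 0.05 × 16/52) = 3.0%, against 1 − exp(−0.05) = 4.9% in controls over 52 weeks.
- Counting the 20-week follow-up: 1 − exp(−2 × 0.05 × 36/52) = 6.7%, against 1 − exp(−0.05 × 72/52) = 6.7%. A doubled hazard looks equal.

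The hazard ratio at which the stopped arms merely look equal to controls is 52/T on treatment and 72/(T + 20) with follow-up:

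| T (weeks) | On treatment | With follow-up |
|---|---|---|
| 8 | 6.5 | 2.6 |
| 16 | 3.25 | 2.0 |
| 24 | 2.2 | 1.6 |
| 36 | 1.4 | 1.3 |

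The follow-up column assumes that the raised hazard persists off drug. Early discontinuation in the retained arms would narrow the gap in both columns.

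**5. Precision of a concurrent comparison.** Assume event risks of 2% in controls and 7% in the pooled stopped arms. The approximate 95% half-width is 1.96 × √[0.02 × 0.98/n + 0.07 × 0.93/285] around a difference of 5.0 points:
- placebo, n = 47.5: ±5.0 points (power about 17%);
- naproxen, n = 142.5: ±3.7 points (about 60%);
- placebo and naproxen pooled, n = 190: ±3.6 points (about 71%).

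Over control risks of 1 to 3% and stopped-arm risks of 5 to 15%, power runs from 5% to 92% against placebo alone, and from 17% to over 99% against the pooled controls. The comparison is for estimation, not for a test.

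**The case against.** The strongest reply is that little is lost. The SAP sentence is introduced as a list of inclusions, so it need not be exhaustive, and table layouts are not visible. The concurrent patients remain in the database and in SAF – Year 1. The 1 mg regimens keep their AA and DA hazard ratios against placebo. The stopped doses were no longer being studied, the data monitoring committee reviews unblinded data in this trial (Protocol 5.1.8 and 5.3.1), and objectives 4 and 5 concern 52 and 104 weeks of administration, which arms cut short can inform only poorly.

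Most of this stands as a limit on the point. A reader might infer that the randomised evidence on dose-related joint harm is lost altogether, or that the planned tables will reverse the true direction. The documents support neither. The 1 mg comparisons are intact, the missing contrast can be built from data already collected, and false reassurance depends on exposure and event rates that are not given. For AA, DA and JR, stopped patients were encouraged to complete follow-up and the end-of-study call, which reduces the imbalance in time at risk.

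The reply does not remove the gap. An unstated comparator is not a planned one, and committee review does not replace reporting. The SAP already applies a concurrent-randomisation rule to 1 mg Q8W efficacy (3.1 and 3.2) but has no counterpart here.

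**Conclusion.** The point holds as a gap in planned reporting. By the set definitions, no specified analysis puts the 285 stopped-arm patients beside the roughly 332 randomised with them. That count rests on the 3:3:3:3:1 ratio and the figure of 285, and the boundary in the two documents must be reconciled before the set can be fixed.

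Comparing crude USMS percentages with SAF – Year 1 could understate risk. The effect is clearest for on-treatment TEAEs, where a hazard ratio between 1.4 and 6.5 could look like no difference over the assumed 8 to 36 weeks. It is smaller, 1.3 to 2.6, for AA, DA and JR counts that include follow-up. These are illustrations under a constant hazard and not estimates for this trial.

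**What to change.** First reconcile when 3:3:3:3:1 ended (SAP 2.1 against the protocol synopsis, 5.1.3 and 7.5). Then define in SAP 3 a concurrent safety set: all treated patients whose actual randomisation date fell while that scheme was in force.

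In SAP 5.8.7:
- Tabulate 3 mg Q4W, 6 mg Q8W, the two pooled, 1 mg Q4W, naproxen and placebo from this set.
- Report TEAEs, AA, DA and JR up to the common date on which dosing in the USMS arms stopped. State that date: the SAP cites an April 2018 recommendation, and Protocol 10.3.1 a May 2018 measure.
- Give exposure-adjusted rates for these outcomes, with Kaplan-Meier curves for AA, DA and JR.
- Give descriptive differences from concurrent naproxen and from placebo, with 95% intervals suited to sparse events, such as Newcombe or exact.
- Show longer follow-up only as supplementary. After the stop date the comparators kept dosing and were seen about every 4 weeks, while the stopped patients had the sparser follow-up schedule (two clinic visits in Protocol Table 1), so both exposure and detection differ.

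The cost is SAP wording and a small amount of programming on existing data. The intervals will be wide, most of all against about 48 placebo patients, and cutting at the stop date reduces event counts further. The text should call the comparison descriptive.

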## **5.9. Analysis of Pharmacokinetic Data**

Summaries of serum concentrations of functional fasinumab will be presented by nominal time point and dose. Concentrations below the LLOQ of the bioanalytical assay will be set to zero when calculating means.

Plots of individual concentrations over time will be presented by actual day (linear and log scales). Plots of mean and/or median serum concentrations of fasinumab will be presented by nominal time (linear and log scales). For linear-scaled plots, concentrations below the LLOQ will be set to zero; for log-scaled plots, concentrations below the LLOQ will be imputed as LLOQ/2.

Relationships between concentrations of fasinumab and efficacy endpoints, safety endpoints, and/or biomarkers may be evaluated, as appropriate.

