#### 7.3.2. Study Drug Discontinuation

Study drug may be temporarily or permanently discontinued due to medical need, as determined by the investigator or the Sponsor and according to the study stopping rules (Section 5.1.8).

Patients who permanently discontinue from study drug will be encouraged to remain in the study and to complete all study procedures and assessments including completion of the diary, the only exception being not receiving study drug (oral and SC). Patients must continue to adhere to the prohibited medication list as per Section 7.7.1. Patients who agree and thus do not withdraw from the study will be asked to return to the clinic for all remaining study visits per Table 1.

Patients who permanently discontinue from study drug and who opt to withdraw from the study will be asked to complete early termination study assessments, per Table 1.

Patients who discontinue from study drug prior to study completion due to an AA (see Section 9.6.1.1) should return to the clinic for all remaining study visits per the visit schedule.

In the event that a patient must undergo JR surgery during the treatment or follow-up periods, he/she will be discontinued from study drug and asked to return to the study site for a pre-operative visit and for follow-up safety evaluations (as described in Section 8.2.3.10) 4 and 20 weeks after surgery. Pre-operative imaging (X-ray and MRI) will be obtained and submitted to the independent adjudication committee for review to ensure that an AA event is not in occurrence. Instructions for the submission process are provided in the study manual.

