- 18. Collection of samples for PK, ADA, high sensitivity C-reactive protein (hs-CRP) and research are mandatory at the time points specified above. In addition, PK, ADA, hs-CRP and research samples may be drawn at any scheduled visit or unscheduled visit if a patient experiences a treatment-related safety TEAE. Samples should be collected prior to SC study drug administration on SC study drug dosing days.
- 19. Research samples should be collected after an overnight (minimum 8 hours) fast.
- 20. Only for patients who provide written informed consent for the optional genomics sub-study. The sample should be collected at the baseline visit but may be collected at any subsequent visit during the study.
- 21. The purpose of this phone contact is to ask the patient if they have had or are scheduled (or on a waiting list) to have a JR. Pre-operative images should be submitted to the central reader for adjudication, if available.
- 22. If the affected joint has undergone JR an X-ray may be substituted from an MRI.
- 23. Patient-reported outcome measures should be completed first at a study visit, prior to any clinical assessments and procedures (eg, blood draws, ECGs, study drug administration).
- 24. Patients who end treatment early but agree to follow/continue to attend regular study visits do not complete the assessments associated with EOT/week 52 at the time they end treatment. Instead, they complete assessments associated with the study visit they are attending at the time they end treatment early.

**Table 2:** Schedule of Events for Year 2

(Only to be followed by patients who participate in Year 2 after they have completed through week 52 [ie, the week 52 visit] in Year 1).

						Yea	r 2 Treatn	nent (52 we	eeks)					
Study Week	Week 52E 	Week 56E	Week 60E	Week 64E	Week 68E	Week 72E	Week 76E	Week 80E	Week 84E	Week 88E	Week 92E	Week 96E	Week 100E	EOT  Week 104E
Study Day	365E	393E	421E	449E	477E	505E	533E	561E	589E	617E	645E	673E	701E	729E
Visit Window (days)	±7	±7	±7	±7	±7	±7	±7	±7	±7	±7	±7	±7	±7	±7
Visit Number	Visit 17E	Visit 18E	Visit 19E	Visit 20E	Visit 21E	Visit 22E	Visit 23E	Visit 24E	Visit 25E	Visit 26E	Visit 27E	Visit 28E	Visit 29E	Visit 30E
Screening/Baseline:														
Inclusion/Exclusion	X													
Informed consent	X													
Treatment														
SC study drug injection 	X	X	X	X	X	X	X	X	X	X	X	X	X	
Dispense acetaminophen/paracetamol	X	X	X	X	X	X	X	X	X	X	X	X	X	

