### **3.6. The Pharmacokinetic (PK) Analysis Set**

The PK analysis set includes all treated patients that had at least 1 non-missing drug concentration result following the first dose of study drug. Patients will be analyzed according to the treatment actually received (as treated).

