18. Collection of samples for PK, ADA, high sensitivity C-reactive protein (hs-CRP) and research are mandatory at the time points specified above. In addition, PK, ADA, hs-CRP and research samples may be drawn at any scheduled visit or unscheduled visit if a patient experiences a treatment-related safety TEAE. Samples should be collected prior to SC study drug administration on SC study drug dosing days.
19. Research samples should be collected after an overnight (minimum 8 hours) fast.
20. Only for patients who provide written informed consent for the optional genomics sub-study. The sample should be collected at the baseline visit but may be collected at any subsequent visit during the study.
21. The purpose of this phone contact is to ask the patient if they have had or are scheduled (or on a waiting list) to have a JR. Pre-operative images should be submitted to the central reader for adjudication, if available.
22. If the affected joint has undergone JR an X-ray may be substituted from an MRI.

23. Patient-reported outcome measures should be completed first at a study visit, prior to any clinical assessments and procedures (eg, blood draws, ECGs, study drug administration).
24. Patients who end treatment early but agree to follow/continue to attend regular study visits do not complete the assessments associated with EOT/week 52 at the time they end treatment. Instead, they complete assessments associated with the study visit they are attending at the time they end treatment early.

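### SAP 5.9 does not separate concentrations sampled after SC drug is permanently stopped, so dose-labelled visit means understate on-treatment fasinumab exposure

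*SAP*

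**What the plan says.** SAP 5.9 has concentrations "presented by nominal time point and dose. Concentrations below the LLOQ of the bioanalytical assay will be set to zero when calculating means". Mean and/or median curves also go by nominal time, while individual curves go by actual day. Protocol 10.4.5 adds that PK receives no formal statistical analysis.

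The population is set in SAP 3.6: "The PK analysis set includes all treated patients that had at least 1 non-missing drug concentration result following the first dose of study drug". This decides which patients count and removes none of their samples.

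On stopping treatment, Protocol 7.3.2 says: "Patients who permanently discontinue from study drug will be encouraged to remain in the study and to complete all study procedures and assessments". Footnote 1 to Protocol Table 1 has these patients follow the visit schedule for the rest of the study. Footnote 24 says of those who stop early but keep attending: "Instead, they complete assessments associated with the study visit they are attending at the time they end treatment early". Their visits therefore keep ordinary labels.

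On sampling, footnote 18 to SAP Table 3 says: "Collection of samples for PK, ADA, high sensitivity C-reactive protein (hs-CRP) and research are mandatory at the time points specified above". It makes no exception for patients off drug. In Year 1, PK samples are due at baseline and Weeks 4, 8, 16, 32, 52, 56 and 72 (Protocol Table 1).

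Elsewhere the plan does separate off-drug data. SAP 5.7.1 leaves post-discontinuation data out of the primary efficacy analysis, and SAP Section 5 ends the on-treatment periods 4 weeks after the last SC dose. Those periods are defined for safety variables, and nothing equivalent is written for PK.

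**The concern.** Secondary objectives 6 and 7 are the PK profile of fasinumab as administered for up to 52 and 104 weeks. A mean labelled 1 mg Q4W at Week 52 that includes patients who stopped injections months before does not describe that profile. Permanent discontinuation only accumulates, so the off-drug share can grow from visit to visit and look like falling exposure on a constant regimen. A reader of the by-visit table could not tell this from a real loss of exposure.

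**Working it through.** The plan states no PK figure to reproduce. The size has to be bounded by mixture arithmetic.

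**Inputs**
- d, the share who have permanently stopped drug. The only rates in the documents are the sample-size allowances in SAP 2.2: 15% up to Week 16 and 30% up to Week 52. Linear interpolation gives 0.15 + 0.15 × 16/36 = 0.217 at Week 32.
- s, the share of stoppers still sampled. Not given; taken from 0 to 1.
- f, a stopper's residual concentration relative to the on-drug mean. Not given; f = 0 means below LLOQ and set to zero.
- For Q4W, the true on-drug pre-dose level is assumed flat from Week 16.

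The dropout rates are a proxy. In the plan's power calculation they act as lost data. For Q8W against placebo (600 v 200, effect size 0.368, two-sided alpha 0.025), shrinking the groups to 510 v 170 gives 97.2% power (stated 97%), and 420 v 140 gives 93.7% (stated 93%). The documents give no rate for patients who are off drug but still giving samples.

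**Formulas**
- Off-drug share of samples: q = d·s / (1 − d + d·s)
- Reported mean / on-drug mean: R = 1 − q(1 − f)

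**Results for 1 mg Q4W**

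| s | f | R, Week 16 | R, Week 32 | R, Week 52 | Apparent fall, Weeks 16 to 52 |
|---|---|---|---|---|---|
| 0 | – | 1.00 | 1.00 | 1.00 | 0% |
| 0.25 | 0 | 0.958 | 0.935 | 0.903 | 5.7% |
| 0.5 | 0 | 0.919 | 0.879 | 0.824 | 10.4% |
| 1 | 0.25 | 0.887 | 0.838 | 0.775 | 12.7% |
| 1 | 0 | 0.850 | 0.783 | 0.700 | 17.6% |

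Worked example, s = 0.5 and f = 0. At Week 16, q = 0.075/0.925 = 0.081. At Week 52, q = 0.15/0.85 = 0.176. The ratio of means is 0.824/0.919 = 0.896, a fall of 10.4%.

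**Medians.** With s = 1, f = 0 and lognormal on-drug levels with an assumed CV of 50%, the reported median is 0.90 of the on-drug median at Week 16 and 0.77 at Week 52. That is a smaller shift than the mean's 0.85 and 0.70. At an assumed CV of 80% the two are close (0.86 and 0.67), so medians do not cure the problem.

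**Below-LLOQ rule.** With s = 1 at Week 52, replacing zero by LLOQ/2 gives 0.70 + 0.30 × L/2, where L is LLOQ as a share of the on-drug mean. For assumed L of 5% to 20%, the ratio moves from 0.70 to only 0.71–0.73.

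**1 mg Q8W.** Samples precede injection. If active doses run from baseline, Weeks 16 and 32 fall 8 weeks after an active dose, and Week 52 falls 4 weeks after the Week 48 dose. On-drug levels therefore rise at Week 52, by 2^(28/t) relative to Week 32 for a half-life of t days under first-order elimination. For assumed t of 14 and 28 days the rise is 4.0-fold and 2.0-fold. Multiplying by 0.700/0.783 (s = 1, f = 0) gives 3.57 and 1.79, a blunted rise.

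**With an on-drug restriction.** q = 0, so R = 1 at every treatment visit.

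**The case against.** The strongest reply is that these are descriptive tables on which no hypothesis or alpha depends, and that the size is unknown. That stands. If dropouts leave altogether they give no samples, and the effect is nil. Some stoppers also leave the treatment-visit PK schedule. Joint-replacement patients are sent to post-operative visits whose table (Protocol Table 3) lists no PK sample, and patients stopped under the amended cardiovascular, renal or antihypertensive criteria go straight to follow-up (Protocol 7.3.2.1). Individual plots by actual day are a partial safeguard, but they do not correct a tabulated mean.

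A reader might infer more than the documents support:
- That setting below-LLOQ values to zero causes the bias. The working shows that it adds little.
- That both regimens would show a decline throughout. At Week 52 that pattern fits Q4W but not Q8W. The fall at Weeks 56 and 72 is genuine washout.
- That the 104-week profile is equally affected. Protocol 6.2.3 admits to Year 2 only patients who did not permanently stop in Year 1 and who received at least 10 of 13 SC doses, so the off-drug share starts afresh.
- That the plan hides or reverses a relation between exposure and arthropathy, or misreads antibody effects. Confirmed arthropathy does stop dosing, so low levels can follow the event. But SAP 5.9 and 5.10.3.1 leave exposure-safety evaluations and concentration plots by antibody status optional, with no metric, sampling time or model. There is no defined analysis to fault.

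**Conclusion.** The point holds in a limited form. As written, off-drug samples enter the Week 16, 32 and 52 means and medians under the dose label, and those summaries understate on-treatment exposure whenever any stopper is sampled with reduced levels. For 1 mg Q4W the apparent fall from Week 16 to Week 52 lies between 0% and about 18%, with d of 15% and 30% as a proxy, s from 0 to 1, and stoppers below LLOQ. Incomplete washout makes it smaller. For 1 mg Q8W the effect at Week 52 is a blunted rise, if active doses run from baseline. The consequence is confined to describing exposure, mainly secondary objective 6. The low cost of the remedy makes the change worth making.

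**What to change.** In SAP 5.9:
- Add by-visit summaries and mean/median plots limited to samples drawn on or before permanent SC discontinuation and within one planned dosing interval, plus the visit window, of the last active injection. Counting from the last active injection matters for Q8W, where placebo injections fall in between. State the limit in days, since each visit may move by 7 days.
- Report the number on drug and the number below LLOQ at each visit.
- Use the same flag in any exposure-response or antibody-exposure plots.
- Keep the all-treated summary as supportive.
- Summarise off-drug samples separately by time since last active injection.

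The cost is SAP wording and one derived flag from dosing dates already collected. There are two downsides. The on-drug summary has fewer samples at late visits. It also conditions on staying on treatment, which may itself depend on exposure, antibodies or adverse events, and this is why the all-treated summary should stay alongside it.
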